15.5 Storage of Clinical Supplies

Acthar and placebo will be maintained in a temperature controlled, secure locked area with restricted access at the study site.

Study drug will be supplied in kits containing the appropriate amount of vials according to the treatment group to which the subject is assigned. Study drug will be stored under refrigeration between 2° to 8°C (36° to 46°F). Please refer to the Pharmacy Manual for complete information regarding storage and accountability of study drug.

15.6 Drug Accountability

In accordance with ICH requirements, the investigator will, at all times, be able to account for all study drug furnished to the study site. A drug accountability record will be maintained for this purpose. The investigator must maintain accurate records indicating dates and quantity of study drug received, to whom it was dispensed (subject-by-subject accounting) and accounts of any study drug accidentally or deliberately destroyed. All unused study drug not involved in immediate subject dosing will be maintained under locked, temperature-controlled storage at the study site.

15.7 Compliance Monitoring

Prior to beginning the administration of study drug, subjects and/or their caregiver will be trained on dosing administration and must exhibit proper technique. Subjects and/or their caregiver will be trained on the completion of the study diary and will complete study diary entries to record all study drug administration and will bring it, along with all study drug kits including used vials to each visit. Each time study drug is dispensed compliance will be encouraged. Subject diary training is an ongoing process as the diary will be reviewed with the subject at each visit to monitor compliance with study drug administration.

16 EFFICACY ASSESSMENTS

[figure not shown]
Efficacy assessments will be evaluated at times specified in the Schedule of Study Events (Table 7-1). Below are general instructions for the administration of these assessments. Specific instructions and questionnaires will be provided in a separate document.

16.1 Telephone Administered Amyotrophic Lateral Sclerosis Functional Rating Scale – Revised

The ALSFRS-R is a validated questionnaire-based scale used extensively as a primary outcome measure in ALS clinical trials and is considered a predictor of survival (Castrillo-Viguera et al, 2010; Cedarbaum and Stambler, 1997; Cedarbaum et al, 1999; Kollewe et al, 2008; Traynor et al, 2004). Subjects are rated on a scale of 0 to 4 for each of 10 aspects of daily function. The ALSFRS-R has been shown to have good inter- and intra-rater reliability when administered by face-to-face and via telephone (Kasarskis et al, 2005; Kaufmann et al, 2007). In this study, a trained independent rater(s) will administer the questionnaire to each subject/subject's caregiver by telephone at specified times.

16.2 Investigator Administered Amyotrophic Lateral Sclerosis Functional Rating Scale – Revised

The ALSFRS-R trained investigator or designee will administer the ALSFRS-R questionnaire in person with the subject or subject's caregiver at specified times during the study.

[figure not shown]

[figure not shown]

16.5 Spirometry

Spirometry will be administered after the subject has rested for at least 5 minutes using the study site's standard equipment and processes (Fallat et al, 1979; Lechtzin, et al, 2002). Spirometry results must include FVC and forced expiratory volume in 1 second (FEV1). In addition slow vital capacity (SVC) will be collected at the Baseline Visit only.

Subjects with FVC < 60% of predicted at the Screening or Baseline Visit are not eligible for the study.

18 SAFETY ASSESSMENTS AND PROCEDURES

The following safety assessments will be evaluated: AEs, physical examinations, clinical laboratory test results (chemistry, hematology, HbA1c, urinalysis, hepatitis serology, IGRA for TB test), vital signs, and C-SSRS. All safety assessments will be performed at times outlined in the Schedule of Study Events ([Table 7-1](#)). Additional (unscheduled) safety assessments may be performed as needed.

18.1 Adverse Events

Adverse events will be recorded from signing of the ICF and followed by the investigator until the AE is resolved or stabilized. Any and all safety measures (which includes standard of care activities) should be provided by the study site to the subject. Any study site follow-up should be documented.

Refer to [Section 21](#) for additional details on the handling of AEs and SAEs.

18.2 Family History of ALS and Neurologic Disease

Family history of ALS and family history of neurologic disease will be collected at the screening visit. Subjects will be asked to identify any family members with a confirmed diagnosis of ALS or a history of neurologic disease including mother, father, son, daughter, sister, brother, maternal and paternal grandmother, maternal and paternal grandfather, maternal and paternal aunt(s), maternal and paternal uncle(s), maternal and paternal cousin(s),

maternal and paternal nephew(s), maternal and paternal niece(s), and any other family members.

18.3 Medical and Surgical History

Medical and surgical history will be obtained at the Screening Visit. Medical history will include a review of the following systems: general, dermatological, respiratory, cardiovascular, gastrointestinal, genitourinary, gynecological, endocrine, musculoskeletal, hematological, neuropsychological, immune (allergies), and head, eyes, ears, nose, and throat. Historical and current medical conditions including date of last menstrual period for female subjects will be recorded. Subjects will specifically be asked for history of stroke (ischemic, hemorrhagic, other/unknown), dementia (dementia of the Alzheimer's type or other), Parkinson's disease, and/or brain tumor.

In addition, the date of onset and the site (limb, bulbar, or limb and bulbar) of first symptom of ALS will be collected.

18.4 Current Medical Conditions

At each visit after screening, subjects will be asked about any changes in medical conditions, specifically new medical conditions and worsening of existing medical conditions. Any changes since the Screening Visit will be recorded as AEs, as appropriate.

18.5 Physical Examination

A complete physical examination will be performed at the Screening Visit and the Week 36/Early Termination Visit. The complete physical examination includes evaluation of the head, eyes, ears, nose, throat, neck (including thyroid), cardiovascular system (including assessment of heart, peripheral pulses, presence or absence of edema), lungs, abdomen (including liver and spleen, bowel sounds), lymph nodes, musculoskeletal system (including spine, joints, muscles) neurological system (including cranial nerves, reflexes, sensation, strength), skin, extremities and other conditions of note.

A limited physical examination, including evaluation of lungs, heart, abdomen, and extremities will be done at all other visits.

The findings of the physical examinations will be recorded.

18.6 Height and Weight

Height will be collected at screening only. Weight will be collected at specified times during the study.

18.7 Vital Signs

Vital signs will be obtained after the subject has been seated for 5 minutes (minimum) and will include systolic and diastolic blood pressures, pulse rate, respiratory rate, and body temperature. The date for all vital sign assessments will be recorded, additionally time will be recorded for blood pressure assessments.

The investigator may perform additional unscheduled vital sign measurements to evaluate or manage a suspected AE. These unscheduled vital sign measurements should be obtained after the subject has been seated for at least 5 minutes, if possible. Unscheduled vital signs will be recorded.

Screening/Baseline Assessments

A subject with systolic blood pressure > 140 mm Hg and diastolic blood pressure > 90 mm Hg (average of 3 assessments) at the Screening or Baseline Visits does not qualify for the study.

On Study Assessments

If an on-study vital sign is not in the site's standard reference range, an AE will be recorded if the investigator determines the change is clinically significant or requires a change in the subject's clinical management.

18.8 Clinical Laboratory Tests (Chemistry, Hematology, Urinalysis, Lipid Panel, HbA1c, Hepatitis Serology, IGRA, Pregnancy Tests, ██████████ ██████████)

The clinical laboratory tests are listed in [Section 32.1](#). All clinical laboratory tests will be done at a central laboratory facility except urine pregnancy (at the site). Specific instructions for collection, processing, storage, and shipment of clinical laboratory samples will be provided in a separate laboratory manual, where appropriate.

Samples for laboratory testing at all visits may be collected under fasted or nonfasted conditions. The date and time of the sample collection must be documented on the laboratory report. Investigators must review and sign laboratory reports. The clinical significance of each laboratory abnormality will be documented. New clinically significant laboratory abnormalities or clinically significant changes in laboratory values will be reported as AEs, as appropriate.

Hematology with differential, serum chemistry, other specific tests, and urinalysis samples will be collected at the specific times starting at screening and throughout the study. Fasting early morning samples are preferred, but a random daytime sample is acceptable.

In addition:

- All female subjects of child-bearing potential will have a serum pregnancy test at the Screening and Week 36/End of Study Visits. Urine pregnancy tests will be done at all other visits throughout the study. Results must be available prior to dosing with protocol mandated study drug. Subjects with positive results will be ineligible for study entry (Screening Visit or Predose) or withdrawn from the study. Any female subject that becomes pregnant during the study will be immediately withdrawn and the pregnancy report as per [Section 21.5](#).

If applicable, the subject's agreement to use contraception throughout their study participation (through the Follow-up Visit) will be documented.

- Lipid panels will be done at specified times during the study. The lipid panel will include total cholesterol, low density lipoprotein (LDL), high density lipoprotein (HDL), and triglycerides.
- HBsAg and HBcAb will be performed at the Screening Visit. Results of these tests must be negative or nonreactive for subjects to qualify for the study.
- HCV will be performed at the Screening Visit. A positive HCV will automatically trigger a HCV PCR analysis. HCV PCR must be < 25 IU/mL to qualify for the study.
- IGRA for TB will be performed at the Screening Visit. Results of this test must be negative for subjects to qualify for the study.
- HbA1c will be performed at the Screening Visit HbA1c must be $\leq 6.5\%$ for subjects to qualify for the study. Additional HbA1c tests will be done at specified times during the study.

- [REDACTED]

Out-of-Range Laboratory Values

[figure not shown]
[figure not shown]
Laboratory values from samples collected at the Screening Visit will be evaluated by the investigator for eligibility of the subject in the study. Clinical laboratory tests may be repeated once to determine subject eligibility.

[figure not shown]
Laboratory values that fall outside the reference range from samples collected during the study or at study exit or early termination will be assessed by the investigator for clinical significance. If the out of range value for samples is deemed clinically significant by the investigator, an AE will be recorded.

18.9 Columbia -Suicide Severity Rating Scale

The C-SSRS is designed to quantify the severity of suicide ideation and behavior ([Posner et al, 2011](#)). The C-SSRS will be administered by the investigator or designee.

When this assessment is required, they should be the first assessment done at any visit (with other investigator completed assessments) and must be completed prior to any study drug dosing.

20 STATISTICAL METHODS AND PLANNED ANALYSIS

20.1 General Considerations

This section provides a general description of the statistical methods to be used in analyzing both safety and efficacy data. The key statistical issues or considerations will be addressed. A more detailed statistical analysis plan will be provided in a separate document that will be finalized prior to interim analysis.

Unless otherwise specified, all statistical tests will be two-sided with a significance level of 0.05. Summary statistics will be provided for all study variables with descriptive statistics (number of observations, mean, standard deviation, median, minimum, and maximum) for numerical (or continuous) variables. Frequency and percentages will be calculated for categorical variables. Data summary and analyses will be performed with SAS 9.2 or higher.

20.2 Analysis Populations

- The Safety Population will include all randomized subjects who receive 1 or more doses of study drug.
- The Modified Intent-to-Treat (mITT) Population will include all enrolled subjects who receive 1 or more doses of study drug and who have at least one postbaseline telephone administered ALSFRS-R.
- The Per-Protocol Population will include the subset of the mITT population who complete the study as per protocol.

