9 BACKGROUND INFORMATION AND RATIONALE

9.1 Overview

First described by Jean-Martin Charcot, amyotrophic lateral sclerosis (ALS) is a progressive neurodegenerative disorder that affects the upper and lower motor neurons in the central nervous system (Goetz, 2000; Mitchell and Borasio, 2007). As upper motor neurons die, there is a loss of communication from the cerebral cortex with symptoms including spasticity and hyper-reflexia. As lower motor neurons die, there is a loss of communication between the brainstem and spinal cord and the muscles, resulting in weakness, muscle atrophy, and fasciculations (Bedlack et al, 2007; Mitchell and Borasio, 2007; Ravits and La Spada, 2009). Symptom expression is dependent on the site of motor neuron loss, with bulbar involvement manifesting as facial weakness, palatal weakness, weakness and fasciculations of the tongue, as well as pseudobulbar symptoms and dysarthria. Limb involvement can start at any spinal level, with spread of motor neuron death typically to the contralateral limb and then through different spinal cord levels (Mitchell and Borasio, 2007; Ravits and La Spada, 2009).

Amyotrophic lateral sclerosis is a relentlessly progressive disease, with mounting disability related to muscle paralysis and eventual death. Although some patients can survive for many years with ALS, up to 70% to 80% die within 5 years of symptoms onset, most commonly due to respiratory failure (Andersen et al, 2005; Beghi et al, 2006; Miller et al, 2009; Mitchell and Borasio, 2007). The incidence of ALS is about 2 in 100,000, and slightly higher in males than

females (Beghi et al, 2006; Berry and Cudkowicz, 2011; Mitchell and Borasio, 2007; Rothstein, 2009). The onset of symptoms in ALS is typically in 5th or 6th decade of life, and onset before 30 years of age is rare (Beghi et al, 2006; Berry and Cudkowicz, 2011; Rothstein, 2009).

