10.2 Secondary Objectives

The secondary objectives of this study are:

- To assess the safety and tolerability of Acthar in subjects with ALS.
- To assess the effect of Acthar on survival in subjects with ALS.
- To assess longitudinal effect of Acthar on functional decline in subjects with ALS
- To assess the longitudinal effect of Acthar on survival in subjects with ALS

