For all “change from baseline” type of secondary endpoints, the same approach as for the primary efficacy endpoint described above will be used.

The primary and secondary endpoints analyses will be performed for the mITT and Per-Protocol populations.

[REDACTED]

[REDACTED]

[REDACTED]

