20.10 Statistical Power and Sample Size Considerations

The primary efficacy analysis will compare the mean telephone administered ALSFRS-R total score change from baseline at Week 36 in the group treated with Acthar to that in the placebo group using mITT analysis population. With 140 mITT subjects in the group treated with Acthar and 70 mITT subjects in the placebo group (210 subjects total), assuming the expected ALSFRS-R total score change from baseline of 6.3 and 9 in Acthar and placebo groups, respectively, the common SD of the ALSFRS-R total score change from baseline at Week 36 of 5.83 (estimated from PRO-ACT database), and dropout rate of 20% prior to Week 36, the study will have at least 80% power to detect the treatment difference at the 0.05 level of significance. Assuming a few subjects might not qualify for the mITT analysis population after randomization, approximately 213 subjects will be enrolled and randomized into Acthar treated group and placebo group in a 2:1 ratio.

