22 SUBJECT DISCONTINUATION OR WITHDRAWAL

22.1 Subject Withdrawal

Subjects who discontinue, or are withdrawn from the study for any reason, will be required to enter the follow-up period and have the Early Termination and Follow-up safety assessments to assess their continued well-being.

Subjects who early terminate for any reason other than withdrawal of consent should be encouraged to continue minimal study participation via telephone contact. In this circumstance, the ALSFRS-R should be administered over the telephone by the site, and any status update should be collected.

The reason for discontinuation will be recorded. A subject may be discontinued from the study for the following medical or administrative reasons:

Withdrawal by Subject

Subjects will be free to discontinue from the study at any time. Subjects who have received at least 1 dose of study drug but do not complete the study will not be replaced.

Investigator Judgment

If, in the opinion of the Investigator, the benefit/risk balance no longer favors continued study participation for any reason, the subject should be withdrawn.

Adverse Event

If a dosed subject suffers an AE that, in the judgment of the investigator, sponsor or MM, presents an unacceptable consequence or risk to the subject, the subject will be discontinued from further participation in the study.

Death

In the event that a subject dies during the study, death will be the reason for discontinuation.

Lost to Follow-up

Every effort should be used to maintain contact with subjects during their participation in the study. A subject may be considered lost to follow-up if there is no response to 3 attempts to reach the subject by telephone and no response to a certified letter sent to the last known address of the subject. Efforts to contact the subject should be noted in source documentation.

Met Withdrawal Criteria

If a subject is noncompliant (eg, has a positive pregnancy or drug screening test), the subject will be discontinued from further participation in the study. Discontinuation is also mandated for safety and/or tolerability issues as outlined in [Section 15.4.1](#).

Other

If the above reasons are not applicable, please use the “Other” option and provide the appropriate reason for subject withdrawal.

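### The Per-Protocol population requires study completion, so the second set of efficacy analyses selects on a post-randomization outcome and can be biased in either direction

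*Combined protocol and SAP*

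**What the plan says.** Section 20.2 (Analysis Populations) and the Synopsis give the same definition: "The Per-Protocol Population will include the subset of the mITT population who complete the study as per protocol". No deviation criteria follow, and neither place says whether the study is complete at Week 36, after the taper and follow-up visit, or at the end of the open label extension.

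Section 20.5.1 gives this set a full second run of the efficacy analyses: "The primary and secondary endpoints analyses will be performed for the mITT and Per-Protocol populations".

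The mITT Population is much wider. It needs one dose of study drug and includes subjects "who have at least one postbaseline telephone administered ALSFRS-R". Section 20.10 powers the primary comparison of Acthar with the result "in the placebo group using mITT analysis population".

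Section 22.1 lists the reasons for discontinuation: withdrawal by the subject, investigator judgment, adverse event, death, loss to follow-up and meeting withdrawal criteria. On death it says: "In the event that a subject dies during the study, death will be the reason for discontinuation". Section 9.1 describes ALS as a disease in which "up to 70% to 80% die within 5 years of symptoms onset", and Section 10.2 includes the objective "To assess the effect of Acthar on survival in subjects with ALS".

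**The concern.** A per-protocol set is meant to ask what the result looks like among subjects treated as intended. This definition asks a different question. A subject who injected every dose and attended every visit until dying at Week 30 is excluded, although nothing in that subject's conduct departed from the protocol. Completion is an outcome of the disease and of treatment tolerability, and the trial tests whether the drug changes the first and expects it to affect the second. Comparing completers is therefore no longer a comparison of the groups as randomized.

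The rule also works against the chosen model. Amendment 2 moved the primary analysis to an MMRM, which uses the visits a subject contributes before leaving. Sections 15.4.1 and 22.1 also ask that early terminators be encouraged to continue telephone ALSFRS-R. Once non-completers are removed from the set, the MMRM has none of their data to use.

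At stake is the reading of the second set of results. A gap between mITT and Per-Protocol could reflect adherence or could reflect who stayed, and the definition does not let a reader separate the two.

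**Working it through.** **Inputs from Section 20.10.** 140 Acthar and 70 placebo mITT subjects; expected declines 6.3 and 9, so the difference is 9 − 6.3 = 2.7; common SD 5.83; dropout 20% before Week 36; at least 80% power. Section 20.1 sets two-sided 0.05. Change is baseline minus postbaseline, so placebo minus Acthar is positive when Acthar is better.

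**The plan's own figure.** Subjects with Week 36 data: 0.8 × 140 = 112 and 0.8 × 70 = 56. SE = 5.83 × √(1/112 + 1/56) = 0.95. Then 2.7/0.95 = 2.83, and power = Φ(2.83 − 1.96) = 80.8% (80.3% by noncentral t). The stated figure reproduces. It does not depend on the Per-Protocol definition.

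**Size of the set.** On the same dropout, Per-Protocol holds at most 112 + 56 = 168 subjects, so at least 210 − 168 = 42 are excluded for not completing. In the pilot (Sections 9.1 and 9.4), 13 + 7 = 20 of 43 subjects, or 46.5%, completed Week 36. At that rate about 98 of 210 would remain. The pilot was open label and included higher-dose arms, so this is context and not a forecast.

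**Bias when progression drives non-completion.** Simulation with 200,000 subjects per arm, random slopes, visits every 4 weeks, Week 36 SD 5.83 and residual SD 1.5 (assumed). The odds of leaving at each visit multiply by e per 5 points of observed decline, or per SD of true slope (both assumed), calibrated to 20% overall. The true difference is 2.7.

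- Leaving by observed decline: completer difference 2.46, a loss of 0.24 (0.24/2.7 = 9%).
- Leaving by true slope: 2.30, a loss of 0.40 (0.40/2.7 = 15%).
- If only half the dropout is related to progression: 2.57 and 2.49.

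Under this mechanism the arms separate without being told to: about 17–18% non-completion on Acthar and 24–25% on placebo. Against the SE of 0.95, the losses are 0.24/0.95 = 0.25 and 0.40/0.95 = 0.42 of one SE. A hypothetical 40% non-completion, a figure the plan does not use, gives 2.25 and 1.98.

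**Bias when the arms' dropout rates are set separately.** Here the Week 36 decline is normal with SD 5.83. The log-odds of non-completion rise by 0.5 to 2 per SD of the subject's own decline (assumed), and each arm is calibrated to its own rate. Ranges run from weak to strong selection.

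| Non-completion, Acthar / placebo | Overall | Completer difference, truth 2.7 | Completer difference, truth 0 |
|---|---|---|---|
| 20% / 20% | 20% | 2.7 | 0.0 |
| 15% / 30% | (21 + 21)/210 = 20% | 2.3 to 1.7 | −0.4 to −1.0 |
| 25% / 10% | (35 + 7)/210 = 20% | 3.1 to 3.7 | 0.4 to 1.0 |
| 30% / 15% | (42 + 10.5)/210 = 25% | 3.1 to 3.7 | 0.4 to 1.0 |

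If leaving is unrelated to decline (slope 0), the completer difference is 2.7 in every row. Bias therefore needs leavers to differ in decline from stayers, and its sign follows how that selection differs between the arms. The first three rows share the plan's 20% dropout and exclude the same 42 subjects, yet they give no bias, attenuation and inflation respectively.

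Both simulations compare raw completer means and not the baseline-adjusted MMRM.

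**The case against.** The strongest reply is that nothing decisive rests on this set. The primary test is powered on mITT, no section gives Per-Protocol a confirmatory role or demands concordance, and Section 20.11.2 examines robustness through other imputation methods. That stands, and it limits the point to a secondary set of analyses.

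A second reply is that Section 20.1 calls the text a general description and promises a separate SAP, where deviation criteria normally sit. This is fair for the missing criteria and for the meaning of completion. It does not answer the main point: the protocol already states completion as the condition of membership.

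A reader might infer that the bias normally runs toward no difference when the drug works. The documents do not support that. It requires non-completion to be mainly progression-driven, and they point to a competing cause: Section 9.4 reports 3 and 7 adverse-event withdrawals in the pilot's low- and high-dose groups, and Section 15.4.1 lists safety reasons for stopping drug. A reader might also infer that agreement or disagreement with mITT becomes uninterpretable. That is too strong: under the progression mechanism at 20% dropout, the bias is under half a standard error.

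Finally, a reader might infer that a Week 36 analysis was meant to depend on events up to Week 84 or 87. The extension is optional, its efficacy endpoints are only summarized descriptively, and Section 12.1.1 treats completion of the 36-week period as a separate step. The wording is ambiguous, but it does not show that intention.

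**Conclusion.** The point holds for the Per-Protocol analyses and should be corrected. It does not touch the mITT primary inference. The stated definition selects on survival and retention and drops partial data from subjects who may have adhered fully until they died or stopped.

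The direction of the bias cannot be fixed from the documents, which give no dropout or death rates by arm:

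- toward no difference, about 2.3 to 2.5 instead of 2.7 at 20% dropout, if progression drives non-completion;
- toward Acthar, if more Acthar subjects leave, for example for tolerability, and leavers tend to be the faster decliners;
- about none, if dropout is equal and similarly selective in both arms.

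The simulated sizes depend on the assumed selection strengths and, in the first simulation, on the assumed residual SD. If survival were analysed on this set, it would by construction contain no deaths before completion. Whether a survival endpoint for the randomized period exists cannot be confirmed, because parts of the endpoint text are blacked out.

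**What to change.** In Section 20.2 and the Synopsis, define the Per-Protocol Population as mITT subjects with no important protocol deviation likely to affect the telephone ALSFRS-R during the 36-week Randomized Treatment Period. State that:

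- completion is not required, and subjects who die or stop early stay in, with their data up to Week 36 or discontinuation in the same MMRM;
- the population refers to the Randomized Treatment Period and not to the extension;
- the qualifying deviations are listed before any unblinding, including the interim analysis of Section 20.9, and subjects are classified blind to treatment;
- the Per-Protocol analyses are supportive.

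The cost is two sentences of text and a blinded deviation review, with no change to sample size or conduct. The downside is a set that includes some subjects with incomplete follow-up, so it relies on the MMRM's missing-data assumption as mITT does. Deviations are also post-randomization events, which is a further reason for the supportive label.
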